RV460 is an exploratory study that will assess the safety, tolerability, and immunogenicity of a vaccine regimen consisting of priming with an Env-C Plasmid DNA vaccine (with or without novel adjuvants) when given with or without adjuvanted HIV Env gp145 C.6980 protein vaccine and boosting with adjuvanted gp145 C.6980 protein with or without the gp120 DNA vaccine. The study will be carried out at the KEMRI/US Army Medical Research Directorate-Africa (USAMRD-A), Clinical Research Centre, Kericho; and 126 healthy adults will be enrolled. Participants enroll randomly into one of seven groups which have 15/3 vaccine/placebo recipients per group. Each participant will receive six injections (prime at week 0, 4, 12; boost at week 20, 32 and 56) followed up for a total of 108 weeks.

Study objectives will be met by the testing of blood samples from all participants. Willing and eligible participants have the option to provide lymph node and mucosal secretion samples (semen, cervicovaginal, rectal), which will provide the data for objectives 2 and the sub-objectives. Exploratory objectives may be met by genetic analysis including but not limited to Human Leukocyte Antigen (HLA) subtyping.

PRECIS

Title

A Randomized, Double-Blind Phase 1 Trial to Evaluate the Safety and Immunogenicity of Priming with Env-C Plasmid DNA Vaccine Alone, with Different Adjuvants, or with an Adjuvanted HIV Env gp145 C.6980 Protein Vaccine and Boosting with the Adjuvanted HIV Env gp145 C.6980 Protein Vaccine with or without the Env-C Plasmid DNA Vaccine in Healthy HIV Uninfected Adults in Kenya

Clinical Phase

Phase 1

Study Duration

Participants are seen in the clinic for 105 weeks following enrollment and randomization. Participants will be contacted by phone once weekly for an additional three weeks to inquire about medically attended adverse events. The total study-related activities may last up to 6 years (2-3 years screening and clinical activities; 2-3 years of laboratory assays and data analyses).

Participants

Healthy, HIV-uninfected male and female volunteers aged 18 to 40 years.

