In study arm 7, co-immunization of Env-C Plasmid DNA and HIV Env gp145 C.6980 protein-based HIV-1 vaccines are administered in the same injection site. This co-immunization strategy using DNA and protein vaccines can improve both humoral and cellular immune antigen-specific immune responses over either vaccination alone or both in series [16], [17], [18] and it can even improve control of viremia after simian immunodeficiency virus (SIV) challenge in a macaque model [18]. Preclinical studies of DNA and protein suggest that colocalizing simultaneous administration of the DNA and protein vaccines may optimize the immune response. In a study in nonhuman primates by Jalal et al., [16] the group that received co-administered DNA and protein had significantly higher levels of Env-binding antibodies (Abs) and higher avidity that persisted compared to the other groups that received either DNA alone or DNA prime with a protein boost. Also, Env-binding Abs and avidity correlated with slower SIV acquisition and in addition, cytotoxic CD4+ effector memory inversely correlated with peak viral load [18]. In another study, the Haigwood group demonstrated in rabbits that DNA + protein co-administration was superior to protein administration alone regarding antibody kinetics, magnitude, avidity, and neutralization potency [19]. A recent study with nonhuman primates reported the co-immunization of DNA vaccines with recombinant Env proteins mixed together with liposomes containing MPLA and imiquimod (TLR4 and TLR7 agonists, respectively) or liposomes containing MPLA and QS21 resulted in robust and durable cellular and humoral immune responses that efficiently disseminated to mucosal sites and protected against simian immunodeficiency virus (SIV) infection [18]. Similarly, in another study of co-immunization using DNA and gp120 formulated in an oil-in-water emulsion containing a TLR4 agonist also resulted in the highest systemic binding and neutralizing antibodies to homologous or heterologous HIV Env as well as the highest Env-

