2.5 STUDY DESIGN

The RV460 trial is an exploratory study that will assess the safety, tolerability, and immunogenicity of different adjuvant formulations in combination with an Env-C Plasmid DNA and HIV Env gp145 C.6980 protein in a prime-boost combination. Enrolled participants will receive 3 doses of Env-C Plasmid DNA as a prime (with or without adjuvants) or admixed with HIV Env gp145 C.6980 protein. The Env-C Plasmid DNA is given alone, formulated with the adjuvant ALF43 (Army Liposome Formulation with Monophosphoryl Lipid A (MPLA) and 43% Cholesterol) adjuvant, or co-administered with the transcutaneous adjuvant dmLT (*E. coli* heat labile enterotoxin) applied at the injection site. The HIV Env gp145 C.6980 protein boost will be mixed with ALF43, Rehydragel® or ALF43 plus Rehydragel®.

Study groups will be assessed for HIV-1 Env-specific antibodies responses elicited by boosting with HIV Env gp145 C.6980 protein adjuvanted with Rehydragel® with or without ALF43. Group 7 will assess whether or not the concept of co-delivery of Env-C Plasmid DNA and HIV Env gp145 C.6980 protein simultaneously will increase the frequency and magnitude of immune responses than Env-C Plasmid DNA given IM alone (after first three vaccinations – Study groups 1 and 2 or as an Env-C Plasmid DNA IM prime, protein IM boost combination as was observed in mice and non-human primates [18], [19, 92, 93].

Table 1: Study Design

Group	n =		Prime at weeks 0, 4, 12	Boost at weeks 20, 32, 56
	V	p		
1	15	3	Env-C Plasmid DNA (2 mg, IM)	HIV Env gp145 C.6980 protein (100 µg, IM)/Rehydragel® (500 µg, IM)

Group	n =		Prime at weeks 0, 4, 12	Boost at weeks 20, 32, 56
	V	p		
2	15	3	Env-C Plasmid DNA (2 mg, IM)	HIV Env gp145 C.6980 protein (100 µg, IM)/Rehydragel® (500 µg, IM)/ALF43 (200 µg, IM)
3	15	3	Env-C Plasmid DNA (2 mg, IM) + dmLT (50 µg, TCI)	HIV Env gp145 C.6980 protein (100 µg, IM)/Rehydragel® (500 µg, IM)
4	15	3	Env-C Plasmid DNA (2 mg, IM) + dmLT (50 µg, TCI)	HIV Env gp145 C.6980 protein (100 µg, IM)/Rehydragel® (500 µg, IM)/ALF43 (200 µg, IM)
5	15	3	Env-C Plasmid DNA (2 mg, IM)/ ALF43 (200 µg, IM)	HIV Env gp145 C.6980 protein (100 µg, IM)/Rehydragel® (500 µg, IM)
6	15	3	Env-C Plasmid DNA (2 mg, IM)/ALF43 (200 µg, IM)	HIV Env gp145 C.6980 protein (100 µg, IM)/Rehydragel® (500 µg, IM)/ALF43 (200 µg, IM)

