7	15	3	Env-C Plasmid DNA (2 mg, IM)/HIV Env gp145 C.6980 protein (100 µg, IM)/ALF43 (200 µg, IM)	Env-C Plasmid DNA (2 mg, IM)/HIV Env gp145 C.6980 protein (100 µg, IM)/ALF43 (200 µg, IM)/Rehydragel® (500 µg, IM)

IM= intramuscular, TCI = transcutaneous immunization; ALF43 (Army Liposome Formulation with Monophosphoryl Lipid A (MPLA) and 43% Cholesterol); v= Vaccine Recipient; p= Placebo

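### Group 7 receives twice the antigen of the serial groups, so its post-boost contrast compares whole regimens and cannot isolate co-delivery

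*Protocol*

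**What the plan says.** Section 2.5 of the protocol says that Group 7 will assess whether giving DNA and gp145 simultaneously increases the frequency and magnitude of immune responses. It gives two reference points. One is DNA alone after the first three vaccinations, with Groups 1 and 2 named. The other is the same antigens given "as an Env-C Plasmid DNA IM prime, protein IM boost combination as was observed in mice and non-human primates". No group number is attached to the second.

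Section 2.1.1 supplies the background: earlier studies suggest that co-immunisation "can improve both humoral and cellular immune antigen-specific immune responses over either vaccination alone or both in series".

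The schedule is common to all groups: "Each participant will receive six injections (prime at week 0, 4, 12; boost at week 20, 32 and 56". Table 1 in section 2.5 (repeated as Table 3 in section 3.3) sets the contents of each injection:

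- Group 7 prime: "Env-C Plasmid DNA (2 mg, IM)/HIV Env gp145 C.6980 protein (100 µg, IM)/ALF43 (200 µg, IM"
- Group 7 boost: "Env-C Plasmid DNA (2 mg, IM)/HIV Env gp145 C.6980 protein (100 µg, IM)/ALF43 (200 µg, IM)/Rehydragel® (500 µg, IM"
- Prime in Groups 5 and 6: "Env-C Plasmid DNA (2 mg, IM)/ ALF43 (200 µg, IM"
- Boost in Groups 2, 4 and 6: "HIV Env gp145 C.6980 protein (100 µg, IM)/Rehydragel® (500 µg, IM)/ALF43 (200 µg, IM"

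Groups 1 to 4 are primed with DNA without ALF43 (Groups 3 and 4 with the dmLT patch). Groups 1, 3 and 5 are boosted with gp145 and Rehydragel without ALF43. No group other than Group 7 receives gp145 in the prime or DNA in the boost.

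**The concern.** Adding both antigens to every visit changes two things at once: whether they are given together, and how many times each is given. Section 2.5 speaks only of the first. The protocol nowhere mentions the difference in total antigen or in number of exposures, and no group gives co-delivery at the serial groups' total antigen.

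The rival explanation is realistic on the protocol's own data. In the rabbit study in section 2.2.2, neutralisation in general appeared only once protein had been given. The co-immunised rabbits, which had protein from the start, showed high titres from week 12. Earlier and more frequent protein is thus a plausible driver in its own right.

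What is at stake is attribution. Someone following section 2.5 as written could credit simultaneity with a difference the design cannot assign to it, and carry that mechanism into a follow-on trial.

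**Working it through.** **1. Per-injection doses.** The mixing steps in section 3.3.1 give, per 1 mL withdrawn:

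- Group 7 prime (3.3.1.7): DNA 0.6 × 4 / 1.2 = 2.0 mg; gp145 0.2 × 600 / 1.2 = 100 µg; ALF43 240 / 1.2 = 200 µg.
- Group 7 boost (3.3.1.13): DNA 0.6 × 4 / 1.2 = 2.0 mg. The intermediate mix holds 0.5 × 600 = 300 µg gp145 and 0.3 × 5 = 1.5 mg aluminium in 1 mL, so gp145 is 0.4 × 300 / 1.2 = 100 µg and Rehydragel 0.4 × 1.5 / 1.2 = 0.5 mg. ALF43 is 240 / 1.2 = 200 µg.
- Group 6 prime (3.3.1.5): DNA 0.6 × 4 / 1.2 = 2.0 mg; ALF43 200 µg.
- Group 6 boost (3.3.1.11): gp145 0.4 × 300 / 1.2 = 100 µg; Rehydragel 0.5 mg; ALF43 200 µg.
- Other products: DNA alone (3.3.1.1) 0.9 × 4 / 1.8 = 2.0 mg; gp145 with Rehydragel (3.3.1.9) 0.3 × 600 / 1.8 = 100 µg.

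The doses in Table 1 reproduce, so the per-injection amount of each antigen is the same in every group that receives it.

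**2. Full-course totals.** Total = dose per injection × number of injections containing it.

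- Group 7: DNA 6 × 2 = 12 mg; gp145 6 × 100 = 600 µg.
- Each of Groups 1 to 6: DNA 3 × 2 = 6 mg; gp145 3 × 100 = 300 µg.
- Ratio: 2.0 for both antigens.

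**3. Cumulative exposure two weeks after the last prime and after each boost, Group 7 v Group 6.**

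| Week | DNA, mg | DNA doses | gp145, µg | gp145 doses | ALF43, µg | Rehydragel, µg |
|---|---|---|---|---|---|---|
| 14 | 6 v 6 | 3 v 3 | 300 v 0 | 3 v 0 | 600 v 600 | 0 v 0 |
| 22 | 8 v 6 (1.33×) | 4 v 3 | 400 v 100 (4×) | 4 v 1 | 800 v 800 | 500 v 500 |
| 34 | 10 v 6 (1.67×) | 5 v 3 | 500 v 200 (2.5×) | 5 v 2 | 1000 v 1000 | 1000 v 1000 |
| 58 | 12 v 6 (2×) | 6 v 3 | 600 v 300 (2×) | 6 v 3 | 1200 v 1200 | 1500 v 1500 |

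The DNA and gp145 columns are the same for every one of Groups 1 to 6. Only Group 6 also matches Group 7 on ALF43 and Rehydragel throughout. In Groups 1 to 5, total ALF43 at week 58 is 0 or 600 µg against 1200 µg.

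**4. What the contrast identifies.** Let c be the effect of simultaneous delivery at fixed antigen exposure, and e the effect of the extra exposures. Then Group 7 minus Group 6 estimates c + e, plus any interaction. Co-delivery and doubled exposure occur together in Group 7 and nowhere else, so no other pair of groups separates c from e.

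**5. Could existing samples separate them?** Antigen totals do coincide across time. Group 7 at week 14 and Group 2 or Group 5 at week 58 have each had 6 mg DNA, 300 µg gp145 and 600 µg ALF43. They differ, however, in Rehydragel (0 v 1500 µg), number of injections (3 v 6), the interval before the last gp145 dose (12 − 4 = 8 v 56 − 32 = 24 weeks) and calendar time. That contrast does not isolate c either.

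**The case against.** The strongest reply is that no formal plan rests on this contrast. No objective or endpoint in sections 1 or 2.6 to 2.7 names co-delivery against serial delivery. The pooled groups in Tables 5 and 6 contain no such pair. Section 7.2.3 says only that group comparisons may be made, unadjusted because they are hypothesis-generating. Section 2.1.1 also gives Group 7 a descriptive purpose: to look at responses with a TLR4 agonist in liposomes. All of this stands and limits the weight of the point.

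Section 2.5 can also be read as comparing strategies over the same six visits, in which case extra exposures are part of the strategy. For that question, Group 7 v Group 6 is sound: both enrol in the Groups 2 to 7 stage and are matched on adjuvants. This stands too, but section 2.5 describes the target as co-delivery and does not say that the comparison is one of regimens.

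Choosing the comparator could be left to a statistical analysis plan, and the unclosed parenthesis in section 2.5 makes it unclear which groups the sentence covers. Granted. But naming a pair later would not make a confounded contrast answer the aim as worded.

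Three stronger readings are tempting and are not supported:

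- A reader might take the section 2.1.1 sentence as this trial's own claim. It summarises earlier studies; the aim is in section 2.5.
- A reader might infer that extra antigen alone should be expected to raise Group 7's response. The protocol gives no size for such an effect, and section 2.1.1 cites two human studies in which co-immunisation brought no increase. The supportable statement is that extra exposure could do so.
- A reader might treat the antigen-matched week 14 v week 58 comparison as the answer to the serial-delivery question. It trades a concurrent, adjuvant-matched contrast for one confounded in other ways.

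**Conclusion.** The point holds as one about attribution. At every post-boost time, Group 7 has had more of both antigens than any serial group: 4, 2.5 and 2 times the gp145 and 1.33, 1.67 and 2 times the DNA at weeks 22, 34 and 58. A higher Group 7 response could reflect co-delivery, added exposure or both, and the design cannot say which.

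It does not follow that the comparison is invalid. Group 7 v Group 6 remains a proper randomised comparison of whole regimens, and a finding of no benefit would still be informative. The post-prime question against DNA alone is outside this point: DNA is equal there (6 mg each), although gp145 and, for Groups 1 and 2, ALF43 differ. The primary safety analysis is untouched.

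The figures assume complete dosing as set out in Table 1. The matter is worth correcting but not critical, because the immunogenicity comparisons are exploratory and unpowered.

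**What to change.** In section 2.5:

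1. Name Group 6 as the post-boost comparator for Group 7, because it matches on ALF43 and Rehydragel at every visit.
2. State that Group 7 v Group 6 estimates the effect of the whole regimen, that is, adding gp145 to the three primes and DNA to the three boosts with doubled antigen exposure, and not the effect of co-delivery alone.

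The week 14 v week 58 comparison should not be offered as the answer to the serial-delivery question. If shown at all, it should be a descriptive supplement with the differences in Rehydragel, interval, number of injections and calendar time stated.

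The cost is a few sentences, with no new visits, samples, participants, doses or schedule. The downside is that the claim the trial can make about co-delivery becomes narrower.

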2.2 SCIENTIFIC RATIONALE

2.2.1 STUDY PRODUCTS AND DOSE JUSTIFICATION

2.2.1.1 Env-C Plasmid DNA (HIV-1 gp120 (93MW965.26) DNA)

The dose of Env-C Plasmid DNA to be used for immunization is 2 mg. This was based on the dose of DNA plasmids (obtained from [name], University of Massachusetts Medical School), that are being used in PDPHV-201401, the NIAID Sponsored Network study HVTN124 (NCT03409276). The 2 mg dose was further selected based on cGMP manufacturing constraints. The maximum DNA concentration that could be obtained with precipitation was 4 mg/ml. The 2 mg dose is approximately twice that of the low dose (1.2 mg) used in the DP6-001 clinical trial [26], [27], which induced significant immune responses to HIV Env. Numerous clinical trials have used DNA vaccines in the 1-8 mg range in HIV vaccine clinical trials [28], [29] [30], [31], [32] [33], [34], [35] and other diseases [36]; for reviews see [37], [38], [39].

2.2.1.2 HIV Env gp145 C.6980 Protein

The dose of HIV Env gp145 C.6980 protein to be used for immunization is 100 µg. The dose of Env protein used in clinical trials has ranged from 5-600 µg [40], [41]. In AVEG 015 (NCT00001042), 50 µg of gp120 was used [42], [43], [44, 45], whereas in RV144 (NCT00223080) 300 µg each of gp120 MN and gp120 A244 were used [46], [47]. The dose of 100 µg matches the lower dose of HIV Env gp145 C.6980 used in the HVTN 122 trial (NCT03382418). Using ALF43 and Rehydragel® as an adjuvant, immune responses similar to those observed in AVEG015 are expected [45]. Based on the concentration of vialled HIV Env gp145 C.6980 (600 µg/ml), 100 µg was selected to allow for the mixing of the vaccine components.

2.2.1.3 ALF43: Army Liposome Formulation—43% Cholesterol

The dose of MPLA in ALF43 to be used for immunization is 200 µg. This was based on previous clinical trials with the ALF43 predecessor L(MPLA), in which approximately 200 µg was used in a Phase I malaria clinical trial [48] and 11 Phase I prostate [49], [50], [51] or colorectal cancer clinical trials [52] and two Phase II prostate clinical trials. The vaccine induced potent immune responses.

2.2.1.4 Recombinant Double Mutant Escherichia coli Heat Labile Toxin (dmLT)

The dose of dmLT to be used in transcutaneous immunization is 50 µg. This was based on the previous clinical trials with transcutaneous immunization using 50 µg of native LT [53], [54], [55], [56], [57]. In addition, the use of dmLT in doses up to 50 µg have been used as an antigen and/or adjuvant in clinical studies [58], [59], [60], [61]; that was recently reviewed [62].

2.2.1.5 Rehydragel® (Aluminum Hydroxide Fluid Gel)

The dose of aluminum in Rehydragel® to be used is 500 µg. This dose was selected to match the 500 µg dose of aluminum that was used in AVEG015 (NCT00001042) in which ALFA was used as an adjuvant [42], [43], [44], [45].

2.2.2 OVERVIEW OF PRE-CLINICAL STUDY RESULTS

RV460 evaluates Env-C Plasmid DNA with the HIV Env gp145 C.6980 protein vaccine combined with different adjuvants. The adjuvants are dmLT, ALF43, and Rehydragel®. Supporting

information detailing the evaluation of the adjuvants, the Env-C Plasmid DNA and HIV Env gp145 C.6980 protein vaccines is provided in the Investigators Brochure (IB), Nonclinical Section.

Each component of the vaccine regimen has both preclinical and clinical data or is part of a larger class of products, which, collectively, have been extensively tested. Although ALF43 has not been used in humans, it is a revised formulation of L(MPLA). ALF43 has reduced levels of phospholipids and cholesterol but maintains the same amount of MPLA. Reports relevant to assessing the potential toxicity and the immunogenicity of the combined Env-C Plasmid DNA prime-protein boost are described in detail in the IB. WRAIR conducted a preclinical rabbit study to evaluate the proposed RV460 vaccine regimen. The purpose of this study was to evaluate the magnitude, frequency and durability of immune responses induced by Env-C Plasmid DNA and HIV Env gp145 C.6980 protein in combination with the adjuvants ALF43, Alhydrogel,® and dmLT. The rabbit immunogenicity for RV460 was evaluated with ELISA. IgG antibodies were measured against HIV Env gp145 C.6980, gp120 (C.ZA.1197MB) proteins as well as against gp70-V1V2 scaffold antigen. All groups of rabbits induced high titers of HIV Env gp145 C.6980, gp120, and gp70V1V2-specific binding IgG, which were maintained at elevated levels 6 months post-immunization. Co-administration of Env-C Plasmid DNA and HIV Env gp145 C.6980 protein resulted in titers of 100,000 after just one immunization. IM Env-C Plasmid DNA immunization with dmLT via TCI caused a delay in the induction of Abs until week 16. Additionally, neutralizing antibodies against tier 1 viruses were also evaluated. Sera from all the groups had cross-clade Tier 1 neutralizing activities (work in progress). Neutralization was observed only after the HIV Env gp145 C.6980 protein boost and declined from week 24 to week 32. However, the Env-C Plasmid DNA/HIV Env gp145 C.6980 protein co-immunization group had high neutralization titers starting at week 12, which appeared to be more durable. Overall, Env-C Plasmid DNA prime/boost vaccine regimen in combination with the ALF43, and dmLT TCI adjuvants led to the generation of high magnitude durable binding Abs and induced potent neutralizing Abs.

Additionally, toxicity and temperature of all rabbits from RV460 pre-clinical study were evaluated. The temperature of rabbits was taken before each immunization, and 6 and 24 hours after immunization. Clinically relevant elevations of temperature were not observed in any of the rabbits immunized with the different vaccine regimens. Blood samples were drawn at Weeks 0, 4, 8, 12, 16, and 20 from all immunized rabbits for blood chemistry and complete blood cell counts. Most of the animals showed blood chemistry levels within normal physiologic range except for a few fluctuations in some animals, which was considered normal by the pathologist. Samples taken after Week 8 indicate that there were no abnormal blood chemistry results in any group after the last Env-C Plasmid DNA prime was received. Additionally, blood cell counts were measured in pre-immunized animals and at 3 days and again at 1 week after each immunization. The complete blood counts of most rabbits were within the normal physiologic range. The overall conclusion from this rabbit study was that the vaccine formulations were immunogenic, and no safety concerns were identified.

Overall, the vaccine formulations were immunogenic and based on the pyrogenicity and toxicity tests conducted side by side with the immunogenicity testing, no abnormal findings or results were observed. Note that ALF43A in combination with a malaria antigen was tested in a GLP rabbit pharmacology-toxicology study without adverse findings.

See *IB* for details of these pre-clinical results.

2.2.3 OVERVIEW OF RELEVANT CLINICAL STUDIES

Of the five components proposed in the RV460 vaccine regimen, both the Env-C Plasmid DNA (IND 17813; HVTN124) and the HIV Env gp145 C.6980 protein (IND 17766; HVTN122) vaccines are in clinical Phase 1 trials. Clinical data on the RV460-specific formulations of Rehydragel® or dmLT are published. The most significant data sets on HIV Env proteins (gp120) with Rehydragel® (AIDS VAX® vaccine), [46], [43], [63], [64], come from efficacy trials where the product was tested alone or in a prime-boost combination with a canarypox DNA vector (RV144) and compared to placebo. dmLT has been tested as both an antigen and adjuvant in an oral vaccine for enterotoxigenic *E. coli* (ETEC) diarrhea [65], [66], [58].

2.2.3.1 Safety and Immunogenicity of the Env-C Plasmid DNA Alone or with an HIV Env Protein Boost Vaccine

DNA plasmid vaccines expressing HIV-1 Env antigens have been tested in multiple clinical studies up to 8.0 mg/dose and have demonstrated an acceptable safety profile when administered alone or with adjuvanted HIV-1 Env proteins [28], [29], [30], [31], [32], [33], [34], [35] and other diseases [36]; for reviews see [37], [38], [39] HIV-1 DNA plasmid vaccines expressing HIV-1 Env antigens are safe and relatively well tolerated in humans. For some HIV-1 DNA Env preparations, pruritus or localized delayed-type hypersensitivity (DTH) reactions have occurred as non-serious, low-grade adverse events (AEs) attributed to the HIV-1 DNA vaccine; but they were not frequent or severe enough to halt their respective studies.

Although the single plasmid of Env-C Plasmid DNA vaccine has not been previously tested in humans, a first generation of the Env-C Plasmid DNA vaccine was tested as a multigene, polyvalent DNA prime-protein boost HIV-1 vaccine, DP6-001, with the same DNA plasmid backbone [26].

In this study, each participant received two vaccine components; three sequential inoculations using a DNA plasmid vaccine administered either intradermally or intramuscularly followed by two sequential inoculations using a protein vaccine. This study involved 2 dose levels of DNA vaccines (1.2 mg [Groups A and B]; 7.2 mg [Group C]) expressing five gp120 Env antigens (HIV-1 clades A, B, C and E) and one Gag antigen (HIV-1 clade C), and a single dose level of the same five recombinant expressed gp120 protein vaccines, produced and purified from CHO cells, and mixed with QS21 adjuvant at the time of injection. Additionally, Group C in the previous trial received more than 3 times the dose of DNA compared to the 2 mg of Env-C Plasmid DNA proposed in RV460.

After each DNA immunization, Grade 1 or 2 fever was common, occurring in up to 42% of DNA vaccine recipients of which Group A (ID) recipients had significantly more frequent injection-site erythema after DNA vaccination than Groups B or C (IM). Local injection site reactions were most common (65% of participants) and included Type IV delayed-type hypersensitivity (DTH) reactions at prior DNA inoculation sites in 12 of 28 (43%) participants after protein vaccination [26]. The erythematous “recall” reactions at prior DNA vaccination sites typically appeared 36 to 72 hours after injection of the DNA (8 milder reactions) and the protein boost (12 mild to severe reactions).

